## 7. Study Setting

Participants from Australia, China, India, Indonesia, Saudi Arabia, South Africa, and the United Kingdom will complete the final survey online.

## 8. Study Population

The study population will include mums, dads, and teachers who have contact with children ages 5 to 10 years old.

## 9. Eligibility Criteria

Inclusion criteria

- be over the age of 18;
- be mums, dads or teachers likely to influence children 5-10 years old; and
- reside in either Australia, China, India, Indonesia, Saudi Arabia, South Africa, or the United Kingdom.

## 10. Study Outcomes

### 10a. Primary Outcome

Participants' responses to the survey items about their hand-hygiene influencing.

### 10b. Secondary/Exploratory Outcomes

Participants' demographics.

Participants' self-reported confidence.

Participants' responses to the survey items about their surface disinfecting.

## 11. Study Procedures

The survey were designed by consulting the literature and area experts and informed by a previous unregistered pilot survey. The items are designed to measure participants' demographics, hand-hygiene influencing, surface disinfecting, and self-reported confidence as described below.

*Design.*

- **Survey Section 1: Information/Consent Sheet. (1 item)**

Participants will be informed about the study and asked to give their informed consent before advancing. The information/consent sheet can be viewed in Appendix B.

- **Survey Section 2: Demographic items. (5 items)**

We will ask about participants' individual differences, age and gender.

Dem-Q1: How many years old are you?

Response Option

[drop down box if possible]

- 17 or fewer years old
- 18 – 30 years old
- 31 – 40 years old
- 40 – 50 years old
- 50 – 60 years old
- 61 – 70 years old
- 70 or more years old

An age-related demographic is necessary to confirm participants are of an acceptable age to take part in the survey, i.e. 18 or older.

If a person says '17 or fewer', they will not continue in the survey.

Dem-Q2: Are you employed as a full-time teacher for children from 5 to 10 years old?

Response Option

- Yes
- No

A teacher-employment item is necessary to ensure we include the planned number of teachers in the final survey (see Table 2 on p. 10).

Dem-Q3: Do you identify as a mum or dad of any children from 5 to 10 years old?

Response Option

- No
- Yes, a mum
- Yes, a dad

This parent item is necessary to ensure we include the planned number of mums and dads in the final survey. (see Table 2 on p. 10).

If a person says 'NO' and did not identify as a teacher in Q2, then they will not continue in the survey

Dem-Q4: With which gender do you identify?

Response Option

- Female
- Male
- Other/Prefer not to say

This is a regularly collected demographic, that we collect here because we cannot and will not use Q3 to infer participants genders. Further gender options, e.g. 'binary', are not included because these options do not translate well to all surveyed countries.

[If not teacher] Dem-Q5: Which one of the following best describes you?

Response Option

- Work full-time
- Work part-time
- Retired
- Full-time Home-maker / parent
- Student
- Unemployed
- Other

The work-related item is desirable attribute to better understand the participants in the survey participants in the survey.

- **Survey Section 3: Hand-hygiene influencing.**

Appendix A presents a list of the domains, their definitions, and survey items about hand-hygiene influencing.

The hand hygiene items will appear in a random order.

In the final survey, we aim to assess each of 11 behavioral determinates using at least 3 items that can be responded to with a 5-point Likert scales, where 1=strongly disagree and 5=strongly agree. Some items will be reverse scored to mitigate acquiescence bias.

- **Survey Section 4: Surface disinfecting.**

Appendix A presents a list of the domains, their definitions and survey items about hand-hygiene influencing.

The surface cleaning items will appear in a random order.

In the final survey, we aim to assess each of 11 behavioral determinates using at least 1 item that can be responded to with a 5-point Likert scales, where 1=strongly disagree and 5=strongly agree. Some items will be reverse scored to mitigate acquiescence bias.

- **Survey Section 5: Self-reported confidence (3 items).**

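### The Dem-Q1 age options overlap at 40, 50 and 70, so the age description of the sample is not well defined at those ages (minor)

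*Combined protocol and SAP*

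**What the plan says.** Section 11 (Study Procedures, Survey Section 2) asks "Dem-Q1: How many years old are you" and offers seven bands. The lowest, "17 or fewer years old", ends the survey for that person. The next is 18 to 30, followed by "31 – 40 years old", "40 – 50 years old", "50 – 60 years old", "61 – 70 years old" and "70 or more years old".

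The reason given for the item is eligibility: "An age-related demographic is necessary to confirm participants are of an acceptable age to take part in the survey, i.e. 18 or older".

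The other four demographic items cover teacher employment, parent status, gender and work status. None of them asks for exact age or date of birth.

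Elsewhere in the document:

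- Section 10b lists demographics among the secondary/exploratory outcomes.
- Section 12b describes demographics with frequencies, percentages, averages and confidence intervals.
- Section 12b also provides for exploratory comparison of individual differences by charts and tests such as ANOVA, and leaves the content of those analyses open.

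**The concern.** Response options for a single-choice item should be mutually exclusive. Here three boundaries are shared by neighbouring bands, while the others (17/18, 30/31 and 60/61) are cleanly separated. The mixture suggests a drafting slip rather than a chosen convention.

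A 40-year-old may tick either of two bands, and both answers are valid as labelled. Two people of the same age can then be counted differently, and the choice may vary between people and between countries. The survey is anonymous (Sections 6 and 11b), so respondents cannot be asked afterwards, and the recorded band does not show who was at a boundary age.

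What is at stake is the reported age distribution, which is part of the planned description of the sample, and any comparison of responses between neighbouring age bands. In such a comparison, mixing people of the same age across two bands would tend to blur a difference.

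**Working it through.** The plan states no figure on this point, so there is nothing to reproduce. The check has three parts.

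**1. Which ages are ambiguous.** Each whole age from 0 to 120 was compared with the seven bands in Section 11, with both limits taken as inclusive, and the matching bands were counted.

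| Age | Bands that fit |
|---|---|
| 40 | 31-40 and 40-50 |
| 50 | 40-50 and 50-60 |
| 70 | 61-70 and 70 or more |
| every other age | exactly one |

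There are no gaps. With 41-50, 51-60 and 71 or more in place of the three overlapping labels, every age from 0 to 120 falls in exactly one band.

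**2. How many respondents.** The planned total comes from Table 2:

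- India: 375 + 375 + 75 = 825.
- Each of the other six countries: 225 + 225 + 75 = 525.
- Total: 825 + 6 x 525 = 3,975.

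The documents give no age distribution, so the share of respondents at an ambiguous age has to be assumed:

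| Assumed share | Of 3,975 | Of 525 (one country) |
|---|---|---|
| 2% | 79.5, about 80 | 10.5 |
| 5% | 198.75, about 199 | 26.25 |
| 8% | 318 | 42 |
| 10% | 397.5, about 400 | 52.5 |

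Two simple age spreads show where the upper part of this range comes from. Ages spread evenly over 25-54 put 2 of 30 single years at 40 or 50: 3,975 x 2/30 = 265, or 6.7%. Ages spread evenly over 31-50 put 2 of 20 there: 3,975 x 2/20 = 397.5, or 10%. Neither spread gives any weight to age 70.

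**3. How far the band percentages could move.** Under the even 25-54 spread (again an assumption), the extremes are:

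- 31-40 holds 9 or 10 of the 30 single years: 30.0% to 33.3%.
- 40-50 holds 9 to 11: 30.0% to 36.7%.
- 50-60 holds 4 or 5 (only ages up to 54 are present): 13.3% to 16.7%.

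These limits need everyone at a boundary age to choose the same way. A mixture of choices falls between them.

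**The case against.** The strongest reply is that nothing confirmatory depends on these bands. The only reason the plan gives for the age item is the 18-or-older check, and the boundary at 17/18 is clean. Age is not a recruitment stratum in Table 2. It is not a term in the factor analysis, and the regression predictors in Section 12b are the domain averages. All of this stands, and it confines the point to description and exploration.

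A reader might go further than the documents allow in three ways:

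- *That respondents aged 40, 50 or 70 are misclassified.* Either answer is correct as labelled. The classification is ambiguous and inconsistent, but not wrong.
- *That the age data cannot be rescued.* The individual bands cannot be repaired, but merging them into 18-30, 31-60 and 61 or more places every eligible age in one group. Detail within the central range is lost.
- *That the plan commits to an age comparison under Objective 4.* Section 4, Section 5c and Section 12b speak of individual differences without naming age. The opening line of Survey Section 2 can be read as including age among them or as listing it separately. An age comparison is plausible, but it is not specified.

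The counts also deserve caution. They are respondents with an ambiguous band, not proven errors. If a convention placed age 40 in the lower band, only those who chose the upper band would be displaced. The total of 3,975 also assumes that every quota fills, although Section 11 closes each country after 30 days even if it is short.

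What survives is that the overlap is in the instrument itself, nothing in the plan resolves it, and the age frequencies would be reported from categories that are not mutually exclusive.

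**Conclusion.** The point holds in a limited form and is of minor priority. Ages 40, 50 and 70 each fit two Dem-Q1 options and exact age is not collected, so respondents of those ages will be classified inconsistently.

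The size is uncertain. About 80 to 400 of 3,975 planned respondents are affected if 2% to 10% are at an ambiguous age. That range is an assumption, not a figure from the plan. Most would be at 40 and 50, on the further assumption that few parents or teachers of children aged 5 to 10 are 70.

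The consequence reaches the age description and any exploratory age comparison, and goes no further. No conclusion about the primary or secondary hypotheses is put at risk.

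**What to change.** Before the items go for translation, change three labels in the English master to 41-50, 51-60 and 71 or more, keeping 18-30, 31-40 and 61-70. Alternatively, collect age in whole years, which the question stem already asks for, and form the bands in analysis. The change belongs in the English master because the Table 1 process checks that meaning is preserved, so a faithful translation would carry the overlap into every language version. The cost is an edit to three response labels. The sample size and planned analyses do not change.

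If data have already been collected, use 18-30, 31-60 and 61 or more for any age comparison. Where the bands are reported as collected, state the overlap at 40, 50 and 70 as a limitation. The cost is lost detail between 31 and 60 and among those aged 61 or more.

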Appendix A also includes three self-confidence items.

The first item regards participants' confidence about how often their children clean their hands when they are present, 0% to 100% of the time. The second item regards participants' confidence about how often their children clean their hands when they are not present, 0% to 100% of the time. The third item regards participants' confidence about how often they clean their own hands, 0% to 100% of the time.

*Translation.*

After creating the initial items in the English language, the research team will ask OpinionHealth to translate them. The same process will occur for the information/consent sheet. The translation process will proceed as describe in Table 1.

Table 1. Translation process

Step	Action
1	The research team will provide OpinionHealth with the initial items.
2	OpinionHealth will translate the items into the non-English language(s)
3	OpinionHealth will back-translate the items to English.
4	OpinionHealth will provide the research team with copies of the translated and back-translated items.
5	The research team will check to be sure that the items' intended meanings have not been lost in translation. If items' meaning are lost, the translation process will be repeated with those items.

---

Opinion is a reputable survey company located in the United Kingdom experienced in conducting online surveys in line with all UK and EU regulations and Market Research Society's Code of Conduct, e.g., GDPR. For more information, a link to Opinion Health's website is provided here:  
[http://opinionhealth.com/about\\_us](http://opinionhealth.com/about_us)

*Active survey.*

OpinionHealth will to recruit participants according to a stratified fashion across countries and demographic characteristics, see Table 2.

Table 2. Participants stratified characteristic

Country	Participants
India	375 mums 375 dads 75 teachers
UK	225 mums 225 dads 75 teachers
China	225 mums 225 dads 75 teachers
Australia	225 mums 225 dads 75 teachers
South Africa	225 mums 225 dads 75 teachers
Indonesia	225 mums 225 dads 75 teachers
Saudi Arabia	225 mums 225 dads 75 teachers

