The first screen of the online survey will inform participants of the study and request their informed consent to take part (see Appendix B). Those who give their informed consent will continue. Participants who complete the survey will be issued with payment to compensate them for their time in an amount equal to approximately 1 GBP in their home countries currency (varies depending on exchange rates), which they can redeem in the form of amazon gift vouchers or via their personal PayPal accounts.

We will stop collecting survey responses in each country after the planned-sample sizes are achieved or 30 days have passed since that country's survey was activated, whichever comes first.

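### The two role-screening questions show the qualifying answer in a paid, anonymous survey, so some false qualification is likely; the teacher cells are the most exposed

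*Combined protocol and SAP*

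**What the plan says.** All of this is in the combined protocol and SAP.

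- **Screening items (section 11, Survey Section 2).** Dem-Q2 is a Yes/No item: "Are you employed as a full-time teacher for children from 5 to 10 years old". Dem-Q3 offers No, mum or dad: "Do you identify as a mum or dad of any children from 5 to 10 years old". Each names the role and age range that qualify.
- **Screen-out rule.** Apart from the age item, only a double No ends the survey: "If a person says 'NO' and did not identify as a teacher in Q2, then they will not continue in the survey".
- **Use of the answers.** They fill the quotas. For Dem-Q2 the stated reason is: "A teacher-employment item is necessary to ensure we include the planned number of teachers in the final survey". In Table 2, six countries have "225 mums 225 dads 75 teachers", and India has 375 mums, 375 dads and 75 teachers.
- **Routing.** Dem-Q5 (work status: full-time, part-time, retired, student and so on) is shown only to people who are not teachers.
- **Payment (section 11, Active survey).** "Participants who complete the survey will be issued with payment to compensate them for their time in an amount equal to approximately 1 GBP".
- **Recruitment.** A survey company will "recruit participants according to a stratified fashion across countries and demographic characteristics". The frame, and any earlier profiling of its members, are not described.
- **Checks (sections 6 and 11b).** No IP address, location or identifying data are collected. The only stated ground for leaving out a response is that it is incomplete. Some items are reverse scored to limit acquiescence bias, but no rule uses them to remove respondents.

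**The concern.** Someone who reads Dem-Q2 or Dem-Q3 can see which answer is wanted. Giving it keeps the respondent in a survey that pays on completion, and no verification is described. The routing weakens the one later cross-check: a Yes to Dem-Q2 skips Dem-Q5, where an answer such as retired or student would contradict it.

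The teacher cells are most at risk because of base rates. If true teachers are rare among those who reach Dem-Q2, a small false-Yes rate in the much larger remainder can supply a sizeable share of the cell. Fieldwork in a country stops once its planned numbers are reached, so false teachers take places that real ones would have filled.

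False teachers would answer items about pupils, a classroom and colleagues that they do not have. They would also report pupils' handwashing percentages, which enter the regression outcome in section 12b. Section 12a already concedes that the teacher cells are small, but that caveat is about size and would not warn a reader about who is in them.

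**Working it through.** The plan states no misclassification rate, so there is no figure to reproduce.

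**Inputs from the documents (Table 2).** Total: India 375 + 375 + 75 = 825; six other countries at 225 + 225 + 75 = 525 each; 825 + 6 × 525 = 3,975. Teachers: 7 × 75 = 525, and 525/3,975 = 13.2%.

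**Assumed inputs.** p is the share of true qualifying teachers among people who reach Dem-Q2. f is the probability that anyone else answers Yes. True teachers are taken always to answer Yes.

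**Formula.** False share of a cell = f(1 − p) / [p + f(1 − p)].

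- p = 3%, f = 0.25%: 0.002425 / 0.032425 = 7.5%, about 6 of 75.
- p = 2%, f = 0.5%: 0.0049 / 0.0249 = 19.7%, about 15 of 75.
- p = 1%, f = 2%: 0.0198 / 0.0298 = 66.4%, about 50 of 75.

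False share (number of 75):

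| p | f = 0.25% | f = 0.5% | f = 1% | f = 2% |
|---|---|---|---|---|
| 1% | 19.8% (15) | 33.1% (25) | 49.7% (37) | 66.4% (50) |
| 2% | 10.9% (8) | 19.7% (15) | 32.9% (25) | 49.5% (37) |
| 3% | 7.5% (6) | 13.9% (10) | 24.4% (18) | 39.3% (29) |
| 10% | 2.2% (2) | 4.3% (3) | 8.3% (6) | 15.3% (11) |
| 30% | 0.6% (0) | 1.2% (1) | 2.3% (2) | 4.5% (3) |
| 50% | 0.2% (0) | 0.5% (0) | 1.0% (1) | 2.0% (1) |

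The first three rows represent an untargeted pool; the last two represent invitees already profiled as teachers.

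**When false teachers are the majority.** This needs f > p/(1 − p): about 1.0% at p = 1%, 2.0% at p = 2% and 3.1% at p = 3%. With f at most 2%, it can happen only when p is below about 2%.

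**Against the plan's own yardstick.** Section 12a relies on at least 30 people per subgroup for exploratory work. In the worst cell of the table, 75 − 50 = 25 true teachers remain; at p = f = 2%, about 38 remain.

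**Parent cells, same formula.** p = 30%, f = 1%: 0.007 / 0.307 = 2.3%. p = 15%, f = 5%: 0.0425 / 0.1925 = 22.1%. At f = 2% the range over p = 15-30% is 4.5% to 10.2%.

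**Dilution.** If half of all teachers were false: 262.5/3,975 = 6.6% of the pooled sample, 37.5/525 = 7.1% of a 525-person country and 37.5/825 = 4.5% of India.

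**The case against.** The strongest reply is that the large figures need an untargeted pool, and no section says the pool is untargeted. Section 11 describes stratified recruitment to cells defined as mums, dads and teachers. That fits a company inviting people it has already profiled at least as well as an open invitation to adults, and in that case the false share is a few per cent at most. This stands, and it is why both ranges must be shown. A reader might infer that the teacher cells will fill largely with non-teachers. The documents do not support that: it needs p of about 1-2% together with f of about 1-2% or more, and neither value is in the plan.

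A reader might also infer that an ineligible person need only answer Yes to be paid. That goes too far. Payment of about 1 GBP comes on completion, after 53 rated items plus the demographic and confidence questions. Nor is Dem-Q2 the only way in: true parents qualify through Dem-Q3 and have no reason to claim to be teachers, and an ineligible person could claim parenthood instead. Applying one f to every non-teacher is therefore a simplification.

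It would likewise be too strong to say that the primary analysis is undermined, or that false respondents would be undetectable. The factor models and regressions are run overall and by country, and none is specific to teachers. Near-opposite items in Appendix A (such as 6 and 8) could expose careless answering, although no rule uses them and a consistent impostor would pass.

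What remains is that the qualifying answers are visible, a Yes to either is enough to continue, no check is described, and the stated teacher limitation covers only cell size.

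**Conclusion.** The point holds as a cheap improvement to the screener, not as an error or contradiction in the plan. Direct questions that name the qualifying role and age range, in an anonymous survey paid on completion, invite some false qualification, and the teacher cells are the most exposed.

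Its size cannot be fixed from the documents. Under assumed values it is about 7.5% to 66% of a 75-teacher cell for an untargeted pool (p 1-3%, f 0.25-2%), and about 0.2% to 4.5% for pre-profiled invitees (p 30-50%, same f). The undescribed sampling frame decides which range applies. The consequence is mainly for teacher estimates and teacher-parent comparisons. The pooled factor model is affected less through teachers, who are 13.2% of it; parent cells also feed it, at an assumed 2% to 22% false. Confidence is medium, because the design facts are clear and the rates are not.

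**What to change.** Replace Dem-Q2 and Dem-Q3 with neutral items in which the qualifying answer is one of several:

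- **Job.** A list of current jobs that includes school teacher, then ages taught (tick all bands that apply). Ask Dem-Q5 of everyone, so that the full-time condition in Dem-Q2 is kept and a contradictory work status becomes visible.
- **Children.** Age bands of any children (none, 0-4, 5-10, 11-17, 18+; tick all that apply), then mum or dad.

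Assign eligibility and quota cell from the answers without showing the rule. The consent sheet comes before screening, and Appendix B is not in the text available for this review. If the sheet or the invitation states the exact qualifying rule, neutral items gain little, so both should avoid stating it as far as informed consent allows.

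**Cost.** Two items become about four, with translation and rerouting of Dem-Q5. Screening is slightly longer; the sample size does not change. The change has to precede fieldwork, because anonymous responses cannot be re-screened afterwards.

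**Limit.** Answers remain self-reported, so this reduces false qualification but does not remove it. As an illustration only, if f fell from 2% to 0.25% (both assumed), false teachers in a cell of 75 would fall from about 50 to 15 at p = 1%, and from about 29 to 6 at p = 3%.
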